 - b) The parameters of the research plan and activities described in this Application;
 - c) The applicable terms of the grant, contract, or other signed funding agreements;
 - d) Applicable laws and regulations, including those protecting the rights, safety and welfare of human subjects.

3. I certify that I am, or my faculty advisor is, sufficiently qualified by education, training and experience to assume responsibility for the proper conduct of this research. I accept responsibility for ensuring that all member of the research team have or will complete human
4. subjects [CITI training](#) before any work with participants or identifiable data / biospecimens begins.
5. I accept responsibility to personally conduct and/or directly supervise this research. I certify that I have sufficient time and resources to properly conduct and/or supervise this research.

B. Ensuring and Maintaining Compliance

1. I will comply with relevant regulatory and institutional reporting requirements, including Brown University's [Reportable Events Policy](#).
2. I understand that it is my responsibility to ensure that any research personnel, including myself, responsible for the design, conduct or reporting of the research declares any conflicts of interest related to this research. I will ensure that any changes that impact my or other research personnel's answers to the questions in PART IX. Conflict of Interest, are reported promptly to Brown's HRPP.
3. I will ensure that prospective agreement and/or informed consent is obtained and a copy is provided to participants, when appropriate.
4. If there are changes to the research described in this Application for Expedited / Full Board IRB Review that may impact the study's classification as Full Board or Expedited research, I will promptly notify the Brown HRPP of such changes.
5. I will notify the Brown HRPP when I have completed all activities involving human subjects or identifiable participant data or identifiable biospecimens.
6. I will maintain approval, as applicable, with collaborative parties, including approvals from other countries or jurisdictions.
7. I will cooperate with any post-approval monitoring or auditing of study activities and/or study records as requested and/or required by the Brown ORI, the Brown IRB, funding entities, sponsors, and/or any federal or state regulatory agencies.

C. Study records, Reports and Documentation

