The current study will explore the preliminary efficacy of Game Plan for PrEP, a web-based intervention to help high-risk men on PrEP adhere to their medication, reduce their alcohol use, and have safe sex. To accomplish this, we will randomize 100 of MSM to receive either (1) GP4PrEP or (2) an attention-matched control (AC). We will use self-report measures of alcohol use collected at 1-, 3-, and 6-months and changes in a biomarker of alcohol use collected at baseline, 3-, and 6-months to explore whether GP4PrEP reduces binge drinking compared with AC. We will also use data from a biomarker of PrEP adherence to explore whether GP4PrEP improves PrEP adherence vs. AC. Finally, we will also explore whether GP4PrEP reduces STI incidence compared to AC.

The aim is to explore preliminary evidence of GP4PrEP's efficacy in reducing heavy drinking and improving PrEP adherence/persistence, and sexually-transmitted infection (STI) incidence among heavy drinking MSM who are on PrEP, but who report a recent history of missing 3 or more consecutive doses.

If your study **ONLY** involves the use of identifiable secondary data / biospecimens, including coded data from which you may be able to ascertain participant identity, skip to [**PART V**](#). Otherwise, please continue to next page.

3. Materials, Methods and Analysis. *The study design, methods and procedures must be adequately described in order for the IRB to understand all activities in which human subjects will participate. The IRB must also be able to differentiate those procedures that are performed for research purposes from those that are performed for routine care or evaluation.*

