In order to explore its efficacy, 100 participants will be randomized to receive either the app or an attention-matched control (AC). We will use self-report measures of alcohol use collected at 1-, 3-, and 6-months and changes in a biomarker of alcohol use collected at baseline, 3-, and 6-months to explore whether GP4PrEP reduces binge drinking compared with AC. We will also use data from a biomarker of PrEP adherence to explore whether GP4PrEP improves PrEP adherence vs. AC. Finally, we will also test whether GP4PrEP participants showed lower rates of STI incidence across the study period compared to AC. A baseline assessment battery will be used to collect data on alcohol and other drug use and factors that can affect medication adherence such as attitudes towards PrEP, barriers and facilitators to taking PrEP, stigma, and beliefs. Follow-up assessments will also assess a number of covariates that may be relevant to PrEP adherence over time, including side effects, health insurance coverage, financial strain, health-related quality of life, and social support. STI incidence at each quarterly routine PrEP care visit will also be collected by extracting this data from participants' electronic medical records. At these visits, participants are tested for Chlamydia and Gonorrhea at genital, rectal, and oral sites, syphilis, and HIV. At-home kits to collect dried blood spot (DBS) samples will be sent to participants at baseline (immediately after they enroll), at 3-months, and 6-months post-enrollment, using procedures used by several national laboratories and in several past studies. DBS samples will be analyzed for TFV-DP levels, a biomarker for adherence to PrEP, as well as phosphatidylethanol (PEth), a biomarker of alcohol consumption. At the Miriam PrEP clinic, limited research staff who are co-located in the clinic will inquire about PrEP patients' potential interest in

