4. Participant Population. *In order to approve research, the IRB must determine that the selection of participants is equitable and reasonably related to the purpose and aims of the research. The IRB must also consider whether adequate safeguards are in place to minimize any risks that are unique to vulnerable populations. To make this determination, the IRB must review all methods and materials used to contact and recruit potential participants, including letters, flyers, emails, etc.*

Criteria for inclusion in this study are: (1) Current male gender, (2) 18+ years old, (3) able to speak and read in English fluently, (4) heavy alcohol use in the past month (>5 drinks on a single occasion or >14 drinks in a week), (5) currently prescribed and actively taking PrEP, and (6) report missing > 3 PrEP doses in a row at least once in the past 3 months. Those who have (1) injected drugs in the past year, (2) screen positive for drug-related disorders, (3) report a history or risk of complicated alcohol withdrawal, or (4) are currently receiving counseling or medications for alcohol or drug addiction will be excluded. Participants must be fluent in English to participate. The target number of participants to be included in the study is 100, 50 in each condition.

5. Recruitment Methods

Participants will be recruited a variety of ways, including social media advertisements, flyers and business cards, and from an existing database, in which potential participants previously expressed interest in participating in various research studies with Smash Labs. Examples of images and text used in online advertisements are attached, as well as advertising palm cards. Initial contact will involve participants completing an online screener to determine their eligibility for the study. If determined eligible, participants will consent online, and give contact info. Research staff will call to verify participants' enrollment, further explain the consent and what's expected of them in the study, and answer any questions the participant may have. Research staff will be trained by PI and project coordinator. Screening data will be destroyed after study completion.

6. Compensation / Reimbursement

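### Does the protocol commit to change scores for the alcohol biomarker, follow-up-only values for self-reported drinking, and adjustment for covariates measured after randomisation?

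*Protocol*

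**What the plan says.** The efficacy sentence appears in Part III, section 2 (Specific Aims and Study Objectives) and again in section 3 (Materials, Methods and Analysis). For self-report it reads "We will use self-report measures of alcohol use collected at 1-, 3-, and 6-months". For the biomarker, phosphatidylethanol (PEth) in dried blood spots, it speaks of "changes in a biomarker of alcohol use collected at baseline, 3-, and 6-months to explore whether GP4PrEP reduces binge drinking compared with AC".

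Section 3 then describes what is measured and when. At baseline, "A baseline assessment battery will be used to collect data on alcohol and other drug use and factors that can affect medication adherence"; attitudes, barriers and facilitators, stigma and beliefs are given as examples of those factors. Later, "Follow-up assessments will also assess a number of covariates that may be relevant to PrEP adherence over time"; the variables named are side effects, insurance coverage, financial strain, quality of life and social support.

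The scale and purpose are also stated. Section 4 says "The target number of participants to be included in the study is 100, 50 in each condition", and section 2 says "The aim is to explore preliminary evidence of GP4PrEP's efficacy in reducing heavy drinking and improving PrEP adherence/persistence".

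The protocol names no statistical model, test, contrast or adjustment set for any outcome.

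**The concern.** One sentence treats two measures of the same behaviour differently. The biomarker is described through its changes, with baseline among its time points. Self-report is described through three follow-up times, with baseline left out. An analyst who took this as an instruction would subtract baseline from PEth and ignore baseline for self-reported drinking. Both are usually less efficient than adjusting the follow-up value for its own baseline, and a change score is worse than ignoring baseline when the correlation is below 0.5. With 50 participants per arm, that would matter.

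The covariate list raises a second worry. *Covariate* is an analysis term, and the five variables are named only under follow-up. Side effects, quality of life or social support could be influenced by the assigned arm, or by drinking and adherence themselves. Adjusting an arm comparison for them could remove part of the effect or create a spurious one, and the contrast would lose the protection of randomisation.

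**Working it through.** **1. What the literal reading would cost.** The protocol states no power, effect size, standard deviation or correlation, so it has no figure to reproduce. The only input taken from it is 50 per arm. Assumed: one continuous outcome, equal variances at both times (set to 1), baseline to follow-up correlation rho, no dropout, two-sided alpha 0.05, 80% power.

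Variance per participant:
- follow-up value only: 1
- change score: 1 + 1 − 2·rho = 2(1 − rho)
- baseline-adjusted (ANCOVA): 1 − rho²

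Sample size relative to ANCOVA:
- change score: 2(1 − rho)/(1 − rho²) = 2/(1 + rho)
- follow-up only: 1/(1 − rho²)

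Detectable difference in SD units: (1.960 + 0.842) × √(2/50) × √variance = 0.560 × √variance.

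| rho | sample vs ANCOVA: change | sample vs ANCOVA: follow-up only | detectable difference: ANCOVA / change / follow-up only | power at 0.5 SD: ANCOVA / change / follow-up only |
|---|---|---|---|---|
| 0.3 | 1.54 | 1.10 | 0.535 / 0.663 / 0.560 | 0.746 / 0.561 / 0.705 |
| 0.5 | 1.33 | 1.33 | 0.485 / 0.560 / 0.560 | 0.823 / 0.705 / 0.705 |
| 0.7 | 1.18 | 1.96 | 0.400 / 0.434 / 0.560 | 0.938 / 0.898 / 0.705 |
| 0.8 | 1.11 | 2.78 | 0.336 / 0.354 / 0.560 | 0.986 / 0.977 / 0.705 |

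The statistical principle is therefore correct. What remains is whether the protocol commits to either inferior analysis.

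**2. Self-report.** The sentence says when the outcomes are collected. In an ANCOVA or a baseline-adjusted longitudinal model, the outcomes are exactly the 1-, 3- and 6-month values, and baseline enters as a covariate. The baseline battery supplies that covariate. Nothing says it will be left out, so the sentence is compatible with the very analysis the concern would prefer.

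**3. Biomarker.** Changes in a marker measured at baseline, 3 and 6 months may mean subtraction. They may equally mean a repeated-measures model with baseline, or follow-up values adjusted for baseline. The text does not choose.

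**4. The different time points.** Part of the asymmetry comes from the collection schedule. Section 3 sends blood-spot kits at baseline, 3 and 6 months only. Section 6 (Compensation / Reimbursement) pays for survey and kit at those three times, and for an online survey alone at 1 month. The lists would differ for that reason whatever model were used.

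**5. Covariates.** The verb is *assess*. No sentence places these variables in a treatment-effect model; they could serve for description or mediation. They are tied to PrEP adherence, and the adherence biomarker is given no adjustment set either. Absence from baseline is not established: the baseline factors are introduced as examples, and the word *also* in the follow-up sentence does not exclude earlier measurement. The instruments are in attachments (the measures document cited in Part IV, Documentation; data collection materials ticked as included in Part VIII) that are not shown.

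**The case for a change.** The strongest case for the concern is that it rests on text that is present. The sentence is repeated, the second time under a heading that includes analysis, and it names baseline for one measure but not for the other. Baseline adjustment is at least as precise as either alternative in large samples, whatever the correlation. Recruiting on recent heavy drinking may lower the correlation, which is where change scores do worst. If the five covariates are not collected at baseline, no later analysis plan can recover them.

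Part of this stands. The wording is uneven, the precision ranking is right, and the five variables are named only under follow-up. But uneven wording does not specify an estimator. Even a change-score or follow-up-only contrast would remain unbiased under randomisation, so that part concerns precision alone, in a trial whose aim is exploratory and which makes no power claim that could be contradicted. The bias argument needs an adjustment that the protocol never states. The data-collection argument needs a gap at baseline that the text leaves open and that cannot be confirmed without the measures document.

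**Conclusion.** The concern does not hold. The protocol fixes neither a change-score analysis, nor a comparison that ignores baseline, nor adjustment for post-randomisation variables. Its description is compatible with follow-up outcomes adjusted for the baseline values that the trial collects. Choosing the model and covariate set is commonly left to the statistical analysis plan, which may exist but is not shown, so its absence from the protocol is no error.

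The factors of 1.54 to 1.11 (change score) and 1.10 to 2.78 (follow-up only) illustrate what inferior choices would cost at assumed correlations of 0.3 to 0.8, with equal variances and a single continuous follow-up. They do not measure a loss in this trial: binge-drinking days are a count, there are two or three follow-ups, and the protocol gives no correlation. This conclusion would change only if an analysis plan were found to prescribe one of those analyses.

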Participants will be paid \$20 for viewing/interacting with the GamePlan website or control videos, \$50 for completing both the online survey and DBS kits (\$15 and \$35, respectively) at baseline, 3- and 6- months, \$25 for and their 1-month online survey, with a bonus of \$50 for completing all study procedures (\$245 total possible). Participants will be paid via ClinCard. They will be mailed a ClinCard, and all study payment will be made within 3 business days of study activity completion.

Some of the services participants will receive are being performed only because they are participating in this research study. These 'research only' services include sampling a few drops of blood. This will be paid for by the study and will not be billed to the participant or their health insurance company.

Other services they will receive during this research study are considered "routine clinical services" that they would have received even if they were not in the research study. Examples include their PrEP medication and refills, follow-up visits with their doctor every 3 months, HIV and STD testing at these visits, and any other laboratory tests provided as a part of monitoring their health while on PrEP (for example, analysis of your urine and blood). These services will be billed to their health insurance company, but participants' will be responsible for paying any deductibles, co-payments, or co-insurance that are a normal part of their health insurance plan. If they do not have health insurance, they will be responsible for those costs.

7. Potential Research Risks / Discomforts to Participants.

In order to approve the research, the IRB must consider the risks posed to participants by the research and any efforts to mitigate those risks. The IRB needs to determine that the risks have been both minimized and are reasonable in relation to the anticipated benefits to participants, as well as to the importance of the knowledge that may be gained. The IRB will also consider whether the informed consent process provides potential participants with an accurate and fair description of the risks or discomforts.

During this study, some of the questions we will ask are about sex, alcohol and drug use, and other sensitive behaviors. These questions might make participants uncomfortable or embarrassed. This discomfort is usually rare and very mild.

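### STI outcomes come only from routine PrEP-visit records, so if GP4PrEP improves persistence and attendance, its arm is tested more and a true STI reduction is attenuated

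*Protocol*

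**What the plan says.** Four parts of Protocol Part III bear on this.

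- **Section 3 (Materials, Methods and Analysis)** makes STI incidence a comparison between arms: "we will also test whether GP4PrEP participants showed lower rates of STI incidence across the study period compared to AC". On the source of the data: "STI incidence at each quarterly routine PrEP care visit will also be collected by extracting this data from" the participants' electronic records. On where the tests take place: "At these visits, participants are tested for Chlamydia and Gonorrhea at genital, rectal, and oral sites, syphilis, and HIV". The mailed blood-spot kits are analysed for a PrEP-adherence marker and an alcohol marker, not for STIs.
- **Section 6 (Compensation / Reimbursement)** classes the visits as routine care that is billed to insurance: "follow-up visits with their doctor every 3 months, HIV and STD testing at these visits". The same list ties monitoring to PrEP use: "any other laboratory tests provided as a part of monitoring their health while on PrEP". The itemised study payments cover the website or videos, surveys, kits and a completion bonus. Clinic attendance is not itemised.
- **Section 2 (Specific Aims and Study Objectives)** sets the aim as preliminary evidence of "GP4PrEP's efficacy in reducing heavy drinking and improving PrEP adherence/persistence, and sexually-transmitted infection (STI) incidence among heavy drinking MSM".
- **Section 4 (Participant Population)** requires men who "report missing > 3 PrEP doses in a row at least once in the past 3 months", and plans 50 men per arm.

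**The concern.** An STI can enter the data only if the man attends a routine PrEP visit and is tested there. A man who stops PrEP or lets his visits lapse has no described route by which a later infection would be recorded. Because persistence is one of the things GP4PrEP is meant to improve, the chance of observing the outcome may differ by arm as a result of the intervention.

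If it does, the STI comparison is shifted against GP4PrEP by its own success on persistence. A null or adverse STI result could then not be told apart from more testing. The alcohol and adherence outcomes do not share this dependence, since they come from online surveys and mailed kits.

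This is more than an analysis choice. An analysis plan can restrict the comparison to tested time only if test dates and negative results were extracted. It cannot use tests done outside PrEP visits if nobody collects them.

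**Working it through.** The protocol states no STI rate, attendance share, effect size, alpha or power, so there is no figure to reproduce. The calculation below is an illustration.

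**From the protocol:** quarterly visits and 6 months of follow-up, hence about two post-enrolment visits; 50 men per arm.

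**Assumed:** each visit is attended independently with probability a; infection risk q is equal in each quarter; attendance is unrelated to infection risk within an arm.

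**Small-risk approximation**

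- *No catch-up* (an infection missed at its own visit is never found): detection is proportional to a.
- *Full catch-up* (a first-quarter infection missed at visit 1 is still found at visit 2): first-quarter infections are found with probability 1 − (1 − a)² = 2a − a², second-quarter infections with probability a. The sum is 3a − a².

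The observed ratio is the true ratio times the detection ratio, GP4PrEP over control.

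*90% vs 75%*
- No catch-up: 0.90/0.75 = 1.20. A true 0.80 appears as 0.80 × 1.20 = 0.96.
- Catch-up: (2.70 − 0.81)/(2.25 − 0.5625) = 1.89/1.6875 = 1.12. A true 0.80 appears as 0.90.

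*85% vs 65%*
- No catch-up: 0.85/0.65 = 1.31. A true 0.80 appears as 1.05.
- Catch-up: (2.55 − 0.7225)/(1.95 − 0.4225) = 1.8275/1.5275 = 1.20. A true 0.80 appears as 0.96.

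*Equal attendance:* the detection ratio is 1 in both cases, so there is no bias.

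**Check without the small-risk approximation.** Assume true 6-month risks of 30% (control) and 20.1% (GP4PrEP), a ratio of 0.67. Then q = 1 − √0.70 = 0.163 and 1 − √0.799 = 0.106. The detected proportion is 1 − (1 − qa)² without catch-up, and a × (6-month risk) + (1 − a) × a × q with it.

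| Attendance, control / GP4PrEP | Observed ratio, catch-up to none |
|---|---|
| 80% / 80% | 0.67 |
| 80% / 85% | 0.69–0.71 |
| 80% / 90% | 0.72–0.75 |
| 70% / 85% | 0.76–0.80 |
| 60% / 90% | 0.87–0.98 |

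With no true effect and a 30% risk, 80% / 90% gives 1.07–1.12 and 60% / 90% gives 1.30–1.46.

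Without catch-up, complete masking needs an attendance ratio equal to one over the true ratio: 1/0.80 = 1.25, or 1/0.67 = 1.49.

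**The case against.** The strongest reply is that the bias is conditional and may be small. Entrants must be taking PrEP, the lapse criterion concerns missed doses rather than missed visits, and the only PrEP measure described for the between-arm comparison is an adherence biomarker. Better dose-taking need not produce more visits over two quarters. This stands: the protocol does not show that attendance will differ, and a gap of 5 to 10 points moves a true 0.67 only to about 0.69–0.75.

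The direction is not guaranteed either. Men may leave PrEP because their risk fell, and men with symptoms may be likelier to attend. The documents settle neither.

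Three stronger readings are tempting, and the text does not support them.

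- *That a real STI reduction will be masked.* This holds only if attendance differs enough. The apparent reversal at 85% vs 65% (1.05) disappears with full catch-up (0.96).
- *That every man is counted for the whole period whether or not he was tested.* Section 3 speaks of rates over the study period but gives no denominator. A tested-time denominator would fit the wording, and that choice may sit in the analysis plan.
- *That men who leave PrEP care still complete the surveys.* The surveys are scheduled for everyone; completion is not known.

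The survey instruments are attached to the application but not shown, so they may already ask about STI tests. Finally, the aim is exploratory. Even with complete testing, 50 per arm gives only about 21% power for 30% vs 20.1% (two-sided 0.05), so a null STI result would say little in any case. That limits the consequence but does not make the ascertainment comparable between arms.

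**Conclusion.** The point holds in conditional form. As described, STI ascertainment depends on attending PrEP care after randomisation, and the intervention aims to improve PrEP persistence. If that raises attendance, the STI contrast is biased towards no benefit: mildly for small gaps in attendance, and up to full masking for large ones. Under the assumed gaps of 15 and 20 points, a true ratio of 0.80 appears as 0.90–0.96 and 0.96–1.05 respectively. These figures rest on assumed attendance, independent visits, and no link between attendance and infection risk within an arm. It is worth correcting because the remedy is cheap and the missing data cannot be recovered afterwards; for an exploratory outcome it does not undermine the trial as a whole.

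**What to change.** In Part III, section 3:

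1. In the 3- and 6-month surveys sent to all randomised men, ask for every STI test since the last survey, with date and result, from any provider and regardless of current PrEP use. If the attached instruments already do this, say so.
2. Extract the date and result of every STI test, negatives included, from any encounter in the record and not only from PrEP visits.
3. Report the number of STI tests and PrEP-visit attendance by arm beside the STI comparison.
4. State, here or in the analysis plan, that untested time is not treated as STI-free.

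The cost is a few survey items and wider extraction with test dates. Wider extraction needs suitable authorisation; Parts VII and VIII currently mark the protected-health-information appendix and the HIPAA authorization as not applicable. Self-report adds error, and the usable denominator becomes smaller.

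These steps reduce the bias without removing it. Men tested nowhere stay unobserved, and restricting to tested time still conditions on who was tested. The STI contrast should therefore be interpreted alongside testing by arm. Only ascertainment of STI status in all randomised men at 3 and 6 months would close the gap, and that is a larger change.

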participating in the study, or will provide them with a palm card (attached) with contact information for the study team. If patients request them to do so, research staff will also provide patients' first names and email addresses to the study team. The study team will email prospective participants a link to an online screening survey that will provide them with more information about the study and, if interested, will ask them to complete a brief survey (< 5 minutes) to assess their eligibility. All online surveys, including those used for screening, consent, baseline, and all follow-ups, will be collected in Qualtrics, which is currently approved to collect and store Level 3 data (e.g., personal health data, HIPAA-protected data, etc.) by Brown University's Computing and Information Systems office. The screening survey will provide real-time feedback about their eligibility, and if prospective participants are eligible and interested, will provide further study information and ask participants to provide informed consent by electronically signing in a provided field. Consent information will be provided in audio or text-based format to ensure participant understanding. Once they provide consent, participants will then be asked to complete a more detailed online baseline assessment, which will take about 30-45 minutes to complete. After they do so, research staff will mail a DBS collection kit to the addresses participants provide. These kits will include a Whatman protein saver card, two personal lancets, two alcohol pads, medical gauze, bandages, and thorough instructions about how to provide the dried blood spot sample. A link to video instructions will also be included in the kit. Once the DBS card has been prepared participants will be instructed to let it dry in ambient air for 4 hours before enclosing the card in a sealable foil biohazard bag, and then seal it in a self-addressed return mailer and drop it in any USPS mailbox to ship it back to the research offices. Once received, DBS cards will be stored in a -20 degree freezer until the end of the study, when they will be shipped on dry ice to the lab for analysis. DBS cards will be marked with that participants' study ID number prior to being shipped to participants so that no identifying information is included on any materials shared with the lab.

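### Could the mailed baseline blood card be collected after a man has already used Game Plan, diluting the PEth change measure?

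*Protocol*

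**What the plan says.** Part III, section 3 (Materials, Methods and Analysis) gives the order of entry: online screening, electronic consent, online baseline survey, then the DBS kit. On the kit it says "After they do so, research staff will mail a DBS collection kit to the addresses participants provide", and that the kits "will be sent to participants at baseline (immediately after they enroll), at 3-months, and 6-months post-enrollment". The man pricks his finger at home, dries the card and is told to "drop it in any USPS mailbox to ship it back to the research offices". Each card carries the "study ID number prior to being shipped to participants". On receipt it is frozen until the end of the study.

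Sections 2 and 3 of Part III both name as a basis for comparing the arms "changes in a biomarker of alcohol use collected at baseline, 3-, and 6-months to explore whether GP4PrEP reduces binge drinking compared with AC". The same cards also supply TFV-DP, the marker of adherence to pre-exposure prophylaxis. The word for change is attached only to the alcohol marker.

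Part III, section 6 (Compensation / Reimbursement) lists $20 "for viewing/interacting with the GamePlan website or control videos" as its own item. It lists $50 at each of baseline, 3 and 6 months "for completing both the online survey and DBS kits", and adds that "all study payment will be made within 3 business days of study activity completion". Neither randomisation nor release of the content has a stated time point.

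**The concern.** The survey and both sets of content are online, while the blood card travels by post. The baseline card must therefore trail the baseline survey by at least the outbound mailing time. If the link to the site went out straight after the survey, a man could work through Game Plan before he pricked his finger. His card would then be a post-intervention sample labelled as baseline.

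The harm would run in one direction. Suppose Game Plan lowers drinking and the control videos do not. An early fall in PEth among late-collecting Game Plan men would be subtracted as if it had been there from the start, and the contrast in change would move towards no effect. PEth is the only alcohol measure described that does not rest on self-report. No later analysis can recover a pre-intervention sample that was never taken. That makes the order of procedures a matter for the protocol, and the silence worth checking.

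**Working it through.** **1. Is there a stated order, and is it wrong?** Setting the sections side by side:

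- Section 3 runs consent, baseline survey, kit, with no intervention step in between.
- Sections 2 and 3 describe the alcohol marker as collected, not merely posted, at baseline.
- Section 6 makes survey and card one baseline item. Its own total confirms this structure: $20 (content) + 3 × $50 (survey $15 plus card $35 at baseline, 3 and 6 months) + $25 (1-month survey) + $50 (bonus) = $245, the stated maximum.
- Section 5 adds a staff call after consent to explain what the study involves. It is not tied to the card.

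No two statements conflict. The text is silent on when content is released, and what it does say points to baseline being completed first.

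**2. What would be lost if the order slipped?** The Protocol states no effect size, standard deviation or power, so only the share of the effect that survives can be shown. Define:

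- p = share of Game Plan men who collect the card after using the site (assumed);
- g = share of the eventual PEth effect already present in those men at collection (assumed);
- b = slope of follow-up on baseline PEth in an adjusted model (assumed);
- control videos have no effect on PEth (assumed).

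Let the true follow-up effect be δ. The Game Plan baseline mean is then shifted by p × g × δ = fδ, with f = p × g. The surviving shares are:

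- raw change score: (δ − fδ)/δ = 1 − f;
- baseline-adjusted model: (δ − b·fδ)/δ = 1 − b·f;
- follow-up level without baseline: 1.

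Of the 50 men planned per arm, p = 10%, 20% and 50% are 5, 10 and 25 men.

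| g | p | f | Change score | Adjusted, b = 0.5 | Adjusted, b = 0.7 |
|---|---|---|---|---|---|
| 0.25 | 10% | 0.025 | 97.5% | 98.75% | 98.25% |
| 0.25 | 20% | 0.05 | 95% | 97.5% | 96.5% |
| 0.25 | 50% | 0.125 | 87.5% | 93.75% | 91.25% |
| 0.5 | 10% | 0.05 | 95% | 97.5% | 96.5% |
| 0.5 | 20% | 0.10 | 90% | 95% | 93% |
| 0.5 | 50% | 0.25 | 75% | 87.5% | 82.5% |
| 1.0 | 10% | 0.10 | 90% | 95% | 93% |
| 1.0 | 20% | 0.20 | 80% | 90% | 86% |
| 1.0 | 50% | 0.50 | 50% | 75% | 65% |

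With p = 0, every entry is 100%. The large losses need half the arm to be late and at least half of the eventual effect to be present already.

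**3. Could it be traced afterwards?** In part. Card and content viewing are separate paid activities, each paid within 3 business days of completion, and cards arrive at the research offices. A card received before the man viewed his content is certainly pre-content. For a card received after viewing, return postage leaves the order unknown unless a collection date was noted.

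**The case for a change.** The strongest case for a change is that a label does not control a process. Calling a card baseline shows intent, but staff posting kits and releasing web links work from operational rules. The Protocol specifies the kit contents and a 4-hour drying time yet does not place the intervention relative to the card. A single sentence would settle it, no analysis can repair a missed sample, and any adherence analysis that uses baseline TFV-DP has the same exposure.

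What stands is that the sequencing rule is unwritten in the text available, and that payment records would repair a lapse only partly. What does not stand is the step from an unwritten rule to a faulty design. The argument needs an unusual reading, in which men receive their assigned content while part of the baseline assessment is outstanding. It also has to assume that the documents not on view are silent. The Protocol refers to written and video kit instructions, and Part VIII marks the data collection and consent materials as attached. The order or a collection date may be there. The sentence about the study ID concerns keeping identifiers from the laboratory and does not list everything written on the card.

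A hard gate would also cost something. Holding back allocation and content until collection is confirmed delays the intervention and may lose men before allocation. Because the later kits are timed from enrolment, it also shortens the interval from content to the 3-month card.

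**Conclusion.** The Protocol leaves a procedural detail unwritten but states nothing wrong. On its ordinary reading the baseline card precedes the content, the PEth change measure is sound and the bias is zero. Staff running the study would be expected to complete baseline, card included, before releasing assigned content, and nothing in the text tells them otherwise.

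If practice departed from that, the loss would be a dilution towards no effect. It would be between 1.25% and 10% of the PEth effect across the tabulated assumptions with one man in ten late, and it would become serious only if about half the arm were late. These figures rest entirely on assumed p, g and b; only the 50 men per arm come from the Protocol. A lapse could hide part of a real effect on one of two alcohol measures in a study that seeks preliminary evidence, but it could not create a false one. Follow-up PEth levels compared without baseline, follow-up self-report and infection incidence would not be touched. No change to the plan is called for.
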